#### 8.4 Interim Analysis

Interim analyses for safety will take place at regular intervals corresponding to the timing of Data and Safety Monitoring Board (DSMB) meetings. For each meeting, the DCC will prepare confidential reports for the DSMB summarizing AEs and SAEs, with statistical comparisons of event rates between treatment groups. Based on the data presented, the DSMB may recommend stopping the study for safety concerns, but there are no formal stopping guidelines for safety for this study.

The percent of treatment responders in each randomized treatment group will also be presented to the DSMB, but no formal interim analyses for efficacy are planned. The primary reason for this is that an interim analysis would be very unlikely to reveal an adequately strong signal in favor of one of the treatment groups for all three of the primary outcomes, and in that case, stopping the study early would prevent some of the primary study questions from being answered. In addition, if the study was stopped early, the smaller sample size that would result would reduce the precision with which we could estimate efficacy among participants who add a supplemental treatment.

#### 9.0 Data and Safety Monitoring and Informed Consent

#### 9.1 Data and Safety Monitoring Board

The protocol will be approved by the DSMB prior to initiation of participant recruitment. The DSMB will also review study data at regularly scheduled meetings either in person or by teleconference. Reports prepared by the DCC for these meetings will include AE and SAE summaries by treatment group and individual SAE narratives. They will also include data on participant recruitment, visit/assessment completion, and adherence to protocol. The DSMB will provide recommendations to NIDDK regarding continuing the study or stopping the study for safety or futility.

## 9.2 Reporting of Adverse Events

All adverse events that occur from the time that the participant is consented through the 3-month follow up visit will be recorded on designated CRFs. Following the 3-month follow up assessment and through the 24-month follow-up assessment, the research coordinators will record only AEs of grade II or higher; however, any AE, regardless of severity/grade, should be reported through the 24-month follow-up visit if it is possibly related to the randomized or optional study treatments. Failure of the study interventions to adequately control fecal incontinence symptoms (failure of efficacy) will be captured by the study endpoints and will not be recorded as an adverse event.

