*4.1.2 Safety:* Adverse events will be collected by participant interview and medical records review, as appropriate, at all clinic and follow-up assessments. Adverse events occurring in the period from the time that the participant is consented through the end of the participant's study involvement at the 24-month follow-up assessment should be documented (See **Section 9.2**). Adverse events will be classified as Serious Adverse Events (SAEs) if conventional criteria are met

or simply as adverse events (AEs). AE

severity will be graded based on common terminology criteria for adverse events (CTCAE). Relationship to treatment will be assessed by the treating clinician and reviewed by the Medical Safety Monitor for the purpose of determining which events need to be reported to the IRB, DSMB and NIDDK in an expedited manner. At the end of the study, relationship to treatment will be evaluated by comparing the incidence of specific AEs between treatment groups. AEs will not be collected on the bowel diary, but patients will be encouraged to contact the study coordinator any time they notice a new symptom or side-effect.

*4.1.3 Cost of care:* A primary endpoint is cost for each treatment from the payer, patient, and societal perspectives. For the payer perspective, we will tabulate the numbers and types of treatment visits and multiply these by Medicare authorized reimbursement rates. Patient costs will be obtained from an *Out-of-Pocket Cost Questionnaire* developed to collect information on amounts patients pay for non-prescription medications and absorbent pads. Estimated costs from the societal perspective will be the sum of payer costs, patient costs, and patients' productivity losses associated with FI as evaluated by the *Work Productivity and Impairment questionnaire* (WPAI). The WPAI is a widely used measure of work absenteeism, impairment while at work, and interference with daily activities.

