#### 8.2 Analysis of Secondary Efficacy Endpoints

Assessment of Efficacy through 24 months. Treatment response (≥75% reduction in weekly FI episodes) at time points through 24 months will be analyzed using a longitudinal extension of the model used for the primary efficacy analysis. Month of assessment, and interaction between month and other predictors, will be included in the model, and the correlation between measures assessed on the same participant over time will be modeled using an appropriate covariance structure. Participants classified as non-responders at 3 months will continue to be considered non-responders at subsequent time points. Participants with missing responses will be classified as non-responders, but sensitivity analyses will be conducted to assess the impact of this assumption.

Assessment of Safety through 24 months. The percentage of participants reporting AEs of pelvic pain of grade II or greater severity, treatment site infection, or an SAE requiring hospitalization by 6, 12, 18, and 24 months will be estimated with 95% confidence intervals using the Wilson Score interval method. Separate estimates will be produced for the groups of participants treated with each of the two therapies alone, and for participants in each of the treatment-order combinations. Confidence intervals will be compared descriptively.

Assessment of Cost of Care through 24 months. The median costs per participant from the perspectives of payers, patients, and society through 24 months will be estimated for each of the treatment groups, including the treatment combinations, using methods described for the primary cost of care endpoint. No formal hypothesis testing will be done, and p-values will be presented for informational purposes only.

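### After month 3, grade I adverse events are recorded only if thought treatment-related, yet incidence between unmasked arms is compared to judge relatedness, without limit on grade or period

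*Combined protocol and SAP*

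**What the plan says.** Section 9.2 sets two recording rules. For the first period: "All adverse events that occur from the time that the participant is consented through the 3-month follow up visit will be recorded". For the second: "Following the 3-month follow up assessment and through the 24-month follow-up assessment, the research coordinators will record only AEs of grade II or higher". It then adds an exception to the second rule: "any AE, regardless of severity/grade, should be reported through the 24-month follow-up visit if it is possibly related to the randomized or optional study treatments". After month 3, then, grade II or higher events are recorded whatever their presumed cause, and grade I events only if someone thinks the treatment may have caused them.

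Section 4.1.2 describes two assessments of causality. During the study, "Relationship to treatment will be assessed by the treating clinician and reviewed by the Medical Safety Monitor", for the stated purpose of deciding which events need expedited reporting. Later, "At the end of the study, relationship to treatment will be evaluated by comparing the incidence of specific AEs between treatment groups". The section does not define which AEs are meant, and gives no grade threshold or time window for that comparison.

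Section 8.4 provides for regular DSMB reports that compare event rates statistically between treatment groups, again without a grade or time limit. It states that there are no formal safety stopping guidelines.

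Section 7.2.2 says that investigators and staff know the assignment. Table 9 (Section 6.4) lists no expected AEs for BIO, and pain at the injection site, bleeding and infection for INJ.

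**The concern.** A between-arm comparison of AE incidence is informative about causality because it does not depend on anyone's opinion of the individual event. That holds only if events are captured in the same way in both arms. For grade I events after month 3, capture depends on an opinion about relatedness, given by people who know the arm and have a written expectation that differs by arm. The comparison is meant to evaluate relatedness, but part of its input has already been filtered on relatedness.

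If a mild late event is more readily considered treatment-related after an injection than after biofeedback training, INJ will show more recorded mild AEs even when the true rates are equal. Review by the Medical Safety Monitor cannot correct this, because events that were never recorded cannot be reviewed. Safety is one of three primary outcomes, and the DSMB works by judgement rather than a formal boundary, so a spurious imbalance could influence how the arms are seen.

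**Working it through.** The plan states no figure for this point, so there is none to reproduce. The check has a logical part and an illustration.

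**Which events are filtered**

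| Period | Grade I | Grade II or higher |
|---|---|---|
| Up to the 3-month visit | recorded regardless of attribution | recorded regardless of attribution |
| Month 3 to 24 | recorded only if possibly related | recorded regardless of attribution |

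One cell of four depends on attribution. The comparison in Section 4.1.2 is not restricted to the other three.

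**Possible size**

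Inputs from the documents: full recording for 3 months and reduced recording for 21 months of a 24-month follow-up (Sections 3.1 and 9.2). Assumptions, none of them in the documents: the same constant true grade I rate λ per month in both arms, and a fixed probability p, by arm, that a grade I event is considered possibly related.

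Expected recorded grade I events per participant over 24 months = λ × (3 + 21p). The ratio of INJ to BIO is (3 + 21·p_INJ) / (3 + 21·p_BIO), and λ cancels.

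| p_BIO | p_INJ | Calculation | Recorded rate ratio (true ratio 1.0) |
|---|---|---|---|
| 10% | 40% | 11.4 / 5.1 | 2.24 |
| 5% | 20% | 7.2 / 4.05 | 1.78 |
| 20% | 40% | 11.4 / 7.2 | 1.58 |
| equal | equal | same numerator and denominator | 1.00 |

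As a percentage of participants with at least one recorded grade I event, 1 − exp(−λ(3 + 21p)) with an assumed λ of 0.03 gives 14.2% at p = 10% and 29.0% at p = 40%. Full recording would give 1 − exp(−0.03 × 24) = 51.3% in either arm.

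**Chance of a nominally significant difference**

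This uses the 78 BIO and 92 INJ participants expected at 3 months (Section 5.2.2), an assumed true post-month-3 grade I proportion of 20% in both arms, and an exact two-sided Fisher test at 0.05. Recorded proportion = 20% × attribution.

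| Attribution, BIO vs INJ | Recorded, BIO vs INJ | Probability of p ≤ 0.05 |
|---|---|---|
| 30% vs 30% | 6% vs 6% | 3.5% |
| 10% vs 30% | 2% vs 6% | 17% |
| 10% vs 50% | 2% vs 10% | 56% |
| 5% vs 60% | 1% vs 12% | 87% |

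Over assumed true proportions of 10% to 30%, the probability ranges from 3% to 98% with these unequal attributions, and from 2.5% to 3.6% with equal attribution. Unequal attribution alone can produce the signal; the documents do not show how unequal it will be.

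**Effect of the proposed restriction**

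Without later grade I events the recorded grade I ratio becomes 3λ / 3λ = 1.0 for any p_BIO and p_INJ.

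**The case against.** The strongest reply is that little of the specified safety analysis is exposed, and most of that stands. The primary safety outcome (Section 8.1) closes at the 3-month assessment, when everything is still recorded. The 24-month composite (Section 8.2) consists of pelvic pain at grade II or above, treatment-site infection and SAEs requiring hospitalization, with confidence intervals compared only descriptively. Pelvic pain sits at the recording threshold and SAEs have their own reporting route.

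It is also fair that the bar is possible relatedness, which is low; that relatedness is assessed during the study as well as at its end; and that the exception was added for safety-reporting compliance. The attribution rates above are assumptions. A single rate per arm is a simplification, since 63 INJ and 17 BIO non-responders are expected to be eligible for another treatment at 3 months (Section 5.4), so later attribution in each arm mixes several treatments. Adding grade II or higher events, which are recorded without regard to attribution, would dilute the ratios.

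A reader might infer three stronger points that the documents do not support:

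- **Relapsed EMM responders.** It might seem that they pass a 3-month visit before randomization, leaving their whole randomized treatment under the reduced rule. Section 3.1 resets their timeline to Time 0 of the randomized treatment, and they have a new 3-month visit.
- **Treatment-site infection.** It has no grade threshold in the composite, so it might seem exposed to the filter. An infection classified as at the treatment site would nearly always count as possibly related in either arm.
- **First versus added treatments.** Section 8.2 says "Separate estimates will be produced for the groups of participants treated with each of the two therapies alone", and also for the treatment-order combinations, but on the composite. No all-grade comparison of first with added treatments is specified.

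What the reply does not remove is the open wording of Sections 4.1.2 and 8.4. If the AEs meant in 4.1.2 are only the listed safety components, the practical effect is small, but the text does not say so.

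**Conclusion.** The concern holds in a limited form. As written, the end-of-study comparison in Section 4.1.2 and the DSMB comparisons in Section 8.4 can include grade I events after month 3 that were entered because unmasked staff considered them possibly related. To that extent the comparisons are partly circular and could show an arm difference where none exists.

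The size cannot be determined from the documents. It rests on attribution differing by arm, which unmasked staff and Table 9 make plausible but do not establish. Illustrative recorded grade I rate ratios run from 1.0 with equal attribution to about 2.2 at 10% versus 40%.

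It would be wrong to conclude that the primary safety test is biased, or that causality is decided only by the final comparison. The primary 3-month outcome and grade II or higher events are not affected, and the 24-month composite is essentially unaffected. The change is still worth making, because it removes the bias at almost no cost.

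**What to change.** In Section 4.1.2, define the AEs to be compared at study end and restrict the between-group incidence comparison to (a) AEs of any grade up to the 3-month assessment, counted from Time 0 of the randomized treatment, and (b) AEs of grade II or higher after that. Apply the same restriction to the between-group comparisons in the DSMB reports under Section 8.4. List later grade I events considered possibly related by arm, without a comparison, and note that their recording depended on attribution.

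Section 9.2 needs no change, and safety reporting continues as it is. The cost is a few sentences in the analysis text and a matching adjustment to the DSMB tables. The downside is that late mild AEs are described but not compared between arms.

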## 9.3 Reporting of Serious Adverse Events

Each clinical investigator is responsible for reporting serious adverse events (SAEs) to the IRB at their institution per local IRB requirements, and to the DCC within 24 hours of when the clinical site is notified of the event. In accordance with GCP, an adverse event is considered "serious" if, in the view of either the investigator or sponsor, it results in any of the following outcomes: death, a life-threatening adverse event, inpatient hospitalization or prolongation of existing hospitalization, a persistent or significant incapacity or substantial disruption of the ability to conduct normal life functions, or a congenital anomaly/birth defect. Important medical events that may not result in death, be life-threatening, or require hospitalization may be considered serious when, based upon appropriate medical judgment, they may jeopardize the patient or subject and may require medical or surgical intervention to prevent one of the outcomes listed in this definition. An adverse event is considered "life-threatening" if, in the view of either the investigator or sponsor, its occurrence places the patient or subject at immediate risk of death. It does not include an adverse event that, had it occurred in a more severe form, might have caused death.

#### Reporting of Unanticipated Adverse Device Effect

Unanticipated adverse device effect means any serious adverse effect on health or safety or any lifethreatening problem or death caused by, or associated with, a device, if that effect, problem, or death was not previously identified in nature, severity, or degree of incidence in the investigational plan or application (including a supplementary plan or application), or any other unanticipated serious problem associated with a device that relates to the rights, safety, or welfare of subjects.

An investigator shall submit to the sponsor and to the reviewing IRB a report of any unanticipated adverse device effect occurring during an investigation as soon as possible, but in no event later than 10 working days after the investigator first learns of the effect. A sponsor who conducts an evaluation of an unanticipated adverse device effect shall report the results of such evaluation to all reviewing IRB's and participating investigators within 10 working days after the sponsor first receives notice of the effect.

Additionally, 21CFR803.1 requires reporting of any required intervention to prevent permanent impairment or damage (applies to devices). This should be reported if the investigator suspects that the use of a medical product may have resulted in a condition which required medical or surgical intervention to preclude permanent impairment or damage to a patient.

Once the SAE is reported to the DCC, it is reviewed by the medical safety monitor (MSM). An SAE summary report is sent to the DSMB and NIDDK (the sponsor). The SAE review process will be documented by the DCC.

Any serious adverse events (SAEs) that are deemed related and unexpected will be submitted in a safety report to the DSMB, NIDDK, and all participating investigators. Clinical sites will follow local IRB guidelines for submission of any unexpected and related SAEs that occur at either their own site or at other study sites.

#### 9.4 Informed Consent

Patients who are candidates for study participation will be approached for enrollment. Written informed consent will be obtained in accordance with IRB Guidelines. A common template for informed consent will be used by all clinical sites, with modifications allowed to meet the necessary requirements of their institutional human subjects committees.

A participant may be prematurely withdrawn from the trial and/or discontinue study treatment as a result of the following:

- At their own request or at the request of their legally acceptable representative.
- If in the investigator's opinion, continuation in the trial would be detrimental to the well-being of the participant.
- If the patient is diagnosed with a condition which is excluded per protocol.
- At the specific request of the sponsor or termination of the study by the sponsor.
- Participant becomes pregnant.

In the event that a participant withdraws consent before completing the study per protocol, attempts will be made to collect the most recently applicable information and follow AEs/SAEs to resolution. If a participant discontinues treatment but does not withdraw consent, all attempts will be made to continue follow up of the participant per protocol.

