  - INJ will include a preparation for treatment and a treatment visit. Preparation will include the use of enemas and minimal restrictions on food intake. Prophylactic antibiotics should be started on the day of the procedure, per the treatment SOP. On the day of the procedure, a physician will inject 1 ml of dextranomer into each of 4 quadrants of the rectum proximal to the dentate line. Ten seconds will be allowed to pass before the injection needle is withdrawn to minimize drainage of the dextranomer. The patient will be scheduled to return in 6 weeks for possible repeat injection of a second 4 ml of dextranomer. At this second appointment, if FI has improved by 75% or more compared to baseline, the patient will be continued without a second injection. However, if the rate of FI is greater than 75% of baseline, the patient will be offered a second injection of dextranomer.
- 4. Combination therapy: The primary assessment of efficacy is at 3 months following the first treatment visit completed, and patients who have not achieved at least a 75% reduction in FI frequency compared to baseline will be classified as treatment failures; they will be invited to choose either the treatment to which they were not randomized or SNS as an adjunctive treatment for the remaining months of the study. One reason for offering non-responders an opportunity to try an additional treatment is to increase the likelihood that patients will consent to be randomized despite possibly having a priori preferences for one of the two treatments. The assumption that this will increase willingness to be enrolled was confirmed in the pilot feasibility survey we performed in 187 patients with FI representing the clinical sites: 57% of patients reported that the ability to receive the treatment of their choice if the assigned treatment was not effective, was important to their willingness to be randomized. Moreover, the estimated 46% of patients who do add a second treatment after the 3 months primary assessment will enable us to collect exploratory data on the possible benefits of combining these treatments. (None of the two investigational treatments can be discontinued.) Thus, the patients

Figure 1. Study Design

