#### 5.1 Inclusion/ Exclusion criteria

Inclusion Criteria	Exclusion Criteria
Physician diagnosis of FI (R15) for the past 6 months or longer. We will recruit some subjects by advertisement who may not have consulted a physician, and this diagnosis may be made by the study physician. Able to ambulate independently on level surfaces. Patient may use	Dementia will be assessed using the Six-Item Screener to Identify Cognitive Impairment. The subject is asked to remember 3 words (apple, table, penny), which may be repeated up to 3 times. This is followed by 3 questions on the year, month, and day of the week. Finally, the subject is asked to recall the three words. Three or more errors has a sensitivity of 88.7% and specificity of 88.0% compared to clinical diagnosis and is not different from the Mini Mental State Exam. [Callahan, CM et al. Six-Item Screener to Identify Cognitive Impairment among Potential Subjects for Clinical Research. Medical Care 2002;40:771-81.] Obstetrical injuries including third and fourth degree tears in the anal sphincter within 6 months.
assistive devices other than parallel bars.	
Average ≥2 solid, liquid, or staining FI episodes per week by self-report and during the two-week baseline	Pregnant or planning pregnancy in next 2 years
Meets criteria for dextranomer treatment except an internal anal sphincter defect of 180 degrees or less is acceptable.	Internal anal sphincter separation >180 degrees on ultrasound or magnetic resonance imaging
Required for randomization: Less than 75% reduction in the number of FI episodes after 4 weeks of EMM.	Spinal cord injury or spina bifida
Age >=18 years	Congenital malformation of anorectum
	Complete rectal prolapse or grade III/IV hemorrhoids
	History of ileoanal pouch; history of anal sphincteroplasty, rectopexy, or rectocele repair within the past 6 months; or history of pelvic surgery with synthetic graft and suspected graft erosion into the anus, rectum, or skin or if the graft ends less than approximately 1" above the upper limit of the anal canal.
	Established diagnosis of inflammatory bowel disease
	Intestinal stoma present
	History of pelvic radiation within previous 12 months or presence of active radiation proctitis.
	Patients who cannot expel the rectal balloon during the balloon expulsion test and who have constipation most of the time.
	Anatomic limitations to placement of dextranomer injections.
	Presence of existing implant in the anorectal region

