	Allergy to hyaluronic acid-based products
	Active anorectal conditions in the last 6 months including abscess, fissures, sepsis, significant bleeding, proctitis, colovaginal and rectovaginal fistulas, anorectal tumors, or other infections.
	If the patient's physician believes it is unsafe for the patient to temporarily stop anticoagulants for any test procedures and treatments associated with the study.
	Patients who have 4 or more days with 4 or more bowel movements classed as a 6 or 7 on the Bristol Stool Scale per day in either (any) week during the Baseline will be excluded.
	Patients with Parkinson's disease, multiple sclerosis, severe diabetic neuropathy documented by EMG, and neurodegenerative disorder.
	Patients currently receiving immunotherapy or chemotherapy
	Significant anal pain in the last 6 months.
	If the patient is unwilling to stop using over-the-counter medications, herbal supplements, or prescribed medications for the purpose of modifying stool consistency, that are not included in the approved medications list (loperamide, laxatives, fiber supplements, and Questran are approved medications), for the duration of the research study.

Medical history will be documented to test for predictors of response.

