*6.3 INJ of dextranomer:* This protocol is a modified version of the protocol used by Graf to ensure consistency across sites and safety of patients. Patients are treated prophylactically with oral antibiotics to minimize injection site infections. One ml of NASHA dextranomer is injected through an anoscope into each quadrant of the submucosa (4 ml total) approximately 5 mm above the dentate line. After each INJ, the needle is left in place for 10 seconds to avoid backward leakage of contrast through the injection channel. Following the INJ patients are counselled to use stool softeners (docusate sodium) until the first bowel movement and to use paracetamol as needed for INJ site discomfort. Prophylactic antibiotics will be administered for 2 days starting on the day of injection. Six weeks after initial INJ, patients return for evaluation, and if the patient has achieved less than 75% reduction in FI, a second INJ is given.

6.4 Comparison of elements of BIO and INJ:

Table 9 shows the elements of the two treatments compared to each	h other.
	rouior.

	Enhanced Medical Management	Biofeedback	Injection
Preparation	None	None	Diet restrictions; enemas; and antibiotics per the procedure SOP
Number of visits	2 visit + 2 phone calls	5-6 visits	2 visits
Visit duration	60 min 1 st visit; 15 min phone calls (Day 3; Day 14); 30 min last visit	60 min	45 min
Visit frequency	1 st and last visits (start of treatment and after treatment program has ended)	Up to 2 visits per week, spaced 2-10 days apart for first 5-6 weeks or so	0 and 6 weeks
Procedure	Daily sphincter exercises, meds to normalize bowel habits	Learn how to improve strength and rectal sensation	Bulking agent injected into rectal wall to narrow opening
Expected Adverse Events	None	None	Pain at injection site, bleeding, infection

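### Section 9.4 permits withdrawal from the trial for a newly diagnosed excluded condition, and these include expected INJ complications, so a safety event can cost follow-up in one arm

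*Combined protocol and SAP*

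**What the plan says.** Section 9.4 opens its list of grounds with "A participant may be prematurely withdrawn from the trial and/or discontinue study treatment as a result of the following". One of the grounds is "If the patient is diagnosed with a condition which is excluded per protocol". Nothing restricts it to conditions present before randomization or unrelated to study treatment.

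The exclusion list in Section 5.1 contains "Active anorectal conditions in the last 6 months including abscess, fissures, sepsis, significant bleeding, proctitis, colovaginal and rectovaginal fistulas, anorectal tumors, or other infections" and, separately, "Significant anal pain in the last 6 months".

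Table 9 (Section 6.4) gives the expected adverse events of INJ as "Pain at injection site, bleeding, infection". Its BIO column says that none are expected.

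Section 8.1 defines the primary safety outcome as pelvic pain of grade II or worse, treatment site infection, or a serious adverse event requiring hospitalization, between randomization and the 3-month assessment. Participants missing safety data are left out of that test. In the efficacy analysis, a participant without a valid 3-month diary is a non-responder.

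Section 9.4 then sets follow-up rules for two situations. If consent is withdrawn, sites try to collect the latest information and follow adverse events to resolution. If treatment is stopped but consent is not withdrawn, follow-up continues per protocol.

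**The concern.** A ground for leaving a trial should not be something that one randomized treatment causes and the other does not. Here an INJ participant with an abscess, an infection, significant bleeding or significant anal pain after injection meets a written ground for being taken out of the trial. The plan expects no such events under BIO.

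Two things are at stake:

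- **Later information.** Safety, cost and quality-of-life data are planned through 24 months. Withdrawal would remove them for participants who had a complication, and those are the participants whose later course bears most on a comparison of safety and cost.
- **The primary efficacy classification.** A participant withdrawn before the 3-month diary becomes a non-responder, whatever their continence would have been.

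Because the rule is discretionary, five sites in an unmasked trial may apply it differently, with withdrawal related to arm and to outcome.

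**Working it through.** **1. Overlap of the lists.**

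| Excluded condition (5.1) | Expected after INJ (Table 9) | Part of the primary safety outcome (8.1) | Expected after BIO (Table 9) |
|---|---|---|---|
| Abscess, sepsis, other infections | Infection | Yes, if at the treatment site or requiring hospitalization | None |
| Significant anal pain | Pain at the injection site | Related component: pelvic pain, grade II or worse | None |
| Significant bleeding | Bleeding | Only if it requires hospitalization | None |

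Section 2.2.2 adds that pain, fever and/or abscess occurred in 9.6% of patients in the cited INJ trial. Significant anal pain is not defined as the same thing as grade II pelvic pain, so the overlap is substantial but not exact.

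**2. Which follow-up rule applies.**

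- Consent withdrawn: covered by Section 9.4.
- Treatment stopped, consent kept: covered by Section 9.4.
- Withdrawn from the trial under the excluded-condition ground, consent kept: no rule.

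**3. The plan's own safety figures.** Inputs from Sections 5.2.2 and 5.4 are 97 randomized per arm, 92 INJ and 78 BIO evaluable, and 9 events against 0.

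- Expected INJ event rate: 9/92 = 9.8%, as stated.
- Power for 0% against 10%, pooled normal approximation, two-sided 0.05 (the plan does not state sidedness): 84.5%. For 0% against 9/92 it is 83.6%. The plan states 83%, so the figure reproduces. Exact power of the named Fisher test is higher, at 90.8% and 89.6%.
- Fisher test on 9/92 against 0/78: p = 0.004.

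These figures do not change as long as a recorded event stays in the analysis. With 0/78 in BIO, significance needs at least 6 events in 92 (6 events: p = 0.032; 5 events: p = 0.063). The test rests on few events, so their classification should be explicit.

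**4. Effect on the efficacy endpoint.** Assume that all 9 expected INJ cases are withdrawn before the 3-month diary. The denominator is the 97 randomized to INJ.

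- Upper bound, if all 9 would have responded: 9/97 = 9.3 points.
- At the 32% INJ response rate in Table 3: 0.32 × 9 = 2.88 responders lost, and 2.88/97 = 3.0 points.
- The trial is sized on a 20-point difference, so 3.0 points is 3.0/20 = 15% of it. The shift lowers the INJ arm only.

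**5. Follow-up at risk.** After the 3-month visit, 24 − 3 = 21 months remain, with assessments at 6, 12, 18 and 24 months. For up to 9 participants that is at most 9 × 21 = 189 participant-months, all in the INJ arm on the plan's expectations.

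**The case against.** The case on the other side is strong on several points.

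- **The rule is permissive.** It allows withdrawal and does not require it, and it allows stopping treatment alone. Section 5.4 assumes at most 5% attrition in INJ, partly because patients will want to be checked for complications. The plan therefore expects to keep these participants. This stands. It limits the likely size, but it does not remove the written ground.
- **The event is normally recorded.** A reader might infer that complications drop out of the 3-month safety comparison and dilute the INJ rate. The documents do not support this. Section 9.2 records all adverse events from consent to the 3-month visit, and Section 9.3 sends serious events to the data coordinating center within 24 hours. A participant with a recorded qualifying event has already met the endpoint. What remains is that Section 8.1 does not say so for someone later withdrawn.
- **The implant criterion.** A reader might infer that every injected participant meets "Presence of existing implant in the anorectal region". This is an entry condition about implants already there. The protocol plans repeat injection and follows INJ participants for 24 months, so the reading fails.
- **No treatment left to stop.** A reader might infer from "None of the two investigational treatments can be discontinued" that for INJ the ground can operate only as withdrawal from the trial. That sentence stands under combination therapy in Section 3.0 and covers both arms. INJ also has a possible second injection at 6 weeks, so stopping treatment has a meaning there.
- **Non-responder classification is the stated intention-to-treat rule**, with sensitivity analyses. This is true. The problem is the arm-linked route into that rule, not the rule itself.
- **Later safety comparisons are descriptive** (Section 8.2). This is also true, and it lowers the stakes for inference, but those estimates still need the data.

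**Conclusion.** The point holds as a defect in a stated rule. Section 9.4 permits withdrawal from the trial because of conditions that overlap the expected complications of INJ and components of the primary safety outcome. None are expected under BIO, and Section 9.4 does not say what data are collected after such a withdrawal if consent stands.

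The size is bounded. On the plan's figures about 9 INJ participants and no BIO participants could be affected by 3 months, provided that their qualifying events are also excluded conditions. Each could lose up to 21 months of later follow-up. If all 9 left before the 3-month diary, the INJ responder proportion would fall by about 3.0 points, assuming that they would have responded at 32%, and by no more than 9.3 points. Losing all 9 is the extreme case, and the documents give no basis for estimating how many sites would withdraw.

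The 3-month safety result and its power are not shown to be at risk, because the triggering event would normally be on record. The change is worth making, as it is cheap and protects data that the plan already intends to collect.

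**What to change.** **Section 9.4.** Separate stopping study treatment from leaving the trial. Under the excluded-condition ground, remove withdrawal from the trial for conditions that arise after randomization, including complications of a study treatment. State that adverse event, cost and outcome follow-up continues to 24 months unless the participant withdraws consent.

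**Section 8.1.** State that a participant with a recorded qualifying event counts as an event in the primary safety analysis, whatever withdrawal follows.

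**Reconcile** Section 9.4 with the exclusion list in Section 5.1, the expected events in Table 9 and the safety definition in Section 8.1. Whether further study treatment is given after a complication is left to the sponsor and the investigator.

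**Cost.** A paragraph of amendment wording, one sentence in Section 8.1 and a memo to sites. The assessments are already in the schedule of activities.
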